9.6. Biomarker Assessment

- [REDACTED]
- [REDACTED]
- [REDACTED]
- [REDACTED]
- [REDACTED]

Longitudinal marker outcome analysis

The above parameters will be summarized by each visit using descriptive statistics for continues variables for the Ex-biomarker Set. In addition, the longitudinal plot of ratio of geometric mean values to baseline visit with 95% CI will be output. The ratio is calculated as geometric mean of each post-treatment visit value divided by baseline visit value. Either change from baseline or percent change from baseline instead of ratio of geometric mean values to baseline visit may be applied for [REDACTED]

Effect of baseline biomarker on efficacy endpoint

- The correlation (scatter) plot between y-axis: change from baseline in ALSFRS-R total score at week 48 and x-axis: baseline value of the above each parameter will be output with the combined MT-1186 treatment group (the daily regimen and the on/off regimen) respectively.

- The KM plot for time to death, tracheostomy or PAV will be output with the combined MT-1186 treatment group (the daily regimen and the on/off regimen) by the subgroup defined by the median baseline value of the above each parameter respectively (>=Median; <Median)

Effect of biomarker change on efficacy endpoint

- The correlation (scatter) plot between y-axis: change from baseline in ALSFRS-R total score at week 48 and x-axis: ratio to baseline at week 48 of the above each parameter will be output with the combined MT-1186 treatment group (the daily regimen and the on/off regimen) respectively. The ratio to baseline at week 48 will be defined by the value at week 48 divided by the baseline value for individual subjects.
Note: Either change from baseline or percent change from baseline instead of ratio of geometric mean values to baseline visit may be applied for [REDACTED]
- The KM plot for time to death, tracheostomy or PAV will be output with the combined MT-1186 treatment group (the daily regimen and the on/off regimen) by the subgroup defined by the median ratio to baseline at week 48 of the above each parameter respectively (>=Median; <Median). The ratio to baseline at week 48 will be defined by the value at week 48 divided by the baseline value for individual subjects.

9.7. Plasma Concentration of Unchanged Edaravone

Plasma concentration of unchanged edaravone data will be listed for subjects who participated in the PK sub-study, and scheduled visit and treatment period with the same precision as provided by the bioanalytical laboratory. PK blood sample collection times, most recent dosing times, as well as derived actual sampling time relative to the most recent dose will be provided in a listing. The actual sampling time relative to the most recent dose will be calculated in hours and rounded to 2 DP.

10. DATA PRESENTATION CONVENTIONS

10.1. Number of Digits to Report

Statistic	Specification	Apply to
Minimum, Maximum	Same number of DPs as the data captured in the datasets	All original (i.e. non-derived)
	see section 8.3	All derived data

Statistical Analysis Plan
Protocol No. MT-1186-A02

Mitsubishi Tanabe Pharma America, Inc.

Mean, Median, SD, SE, CIs	One more DP than used for Min Max	All
Percentages ^{*1}	1 DP	All
Ratios	3 DPs	All
p-values ^{*2}	3 DPs	All

*¹ Percentages: use 1 place after the decimal point, except for the following cases:

If the percentage is equal to 0, then use "(0)" without a decimal

If the percentage is equal to 100, then use "(100)" without a decimal

*² p-values: use 3 places beyond the decimal point, except for the following cases:

If the p-value is less than 0.001, then use p<0.001

10.2. Treatments to Report

Treatment	For TFLs
Oral edaravone 105 mg administered once daily	Edaravone 105 mg once daily
MT-1186 105 mg oral dose, administered for 10 days out of a 14-day period, followed by 2 weeks of matching placebo for 12 treatment cycles (on/off) for a total of 48 weeks	Edaravone 105 mg on/off

10.3. Analysis Visits to Report**Efficacy:**

Analysis Visit	Apply to
Screening	All efficacy
Baseline	All efficacy
Week 4	All efficacy
Week 8	All efficacy
Week 12	All efficacy
Week 24	All efficacy
Week 36	All efficacy
Week 48	All efficacy

Safety:

Analysis Visit	Apply to	Laboratory Tests	Vital Signs	12-Lead ECGs	C-SSRS
Screening	X	X	X	X	
Baseline	X	X	X	X	
Day 8	X (only for Japan)				
Week 4	X	X			X
Week 8	X	X			
Week 12	X	X			X
Week 24	X	X	X		X
Week 36	X	X			
Week 48	X	X	X		X

11. CHANGE FROM THE PROTOCOL

- The number and percentage of subjects with abnormal physical examinations by body system will not be summarized at each visit. This is because physical examination is measured only whether a physical examination or body system evaluation is performed or not. If any significant abnormality started, it will be record in medical history or AE.
- The FAS flag definition will be changed from “all randomized subjects who received at least 1 dose of study medication and had any efficacy data collected after randomization” to “all randomized subjects who received at least 1 dose of study medication” because all randomized subjects who randomized and received at least 1 dose of study medication should be analyzed regardless of post baseline efficacy data in order to estimate treatment effect properly.

12. SOFTWARE

All statistical analyses will be performed using SAS version 9.4 or higher.


Statistical Analysis Plan
Protocol No. MT-1186-A02

Mitsubishi Tanabe Pharma America, Inc.

13. Crispin Jenkinson, Robert Harris & Ray Fitzpatrick (2007) The Amyotrophic Lateral Sclerosis Assessment Questionnaire (ALSAQ-40): Evidence for a method of imputing missing data, *Amyotrophic Lateral Sclerosis*, 8:2, 90-95, DOI: 10.1080/17482960600989343

**APPENDIX 1 INTERIM ANALYSIS SIMULATION RESULT AND DECISION
MAKING PROCESS**

The table below provides the operating characteristics results to Lan and DeMets O'Brein-Fleming stopping boundaries for futility to detect treatment difference at Week 48 when comparing 105 oral edaravone once daily (Test Group) to edaravone 105 mg oral dose on/off (Control Group). The following assumption, using EAST software version 6 were used.

- One sided type I error of 0.025
- Total sample size of 266 completers, taking into account 190 subjects randomized per arm and 30% dropout rate up to Week 48
- Delta of 2.6 units in ALSFRS between Test group to control group with SD of 7.0
- Non-binding for type I error rate
- Lan and DeMets with O'Brein-Fleming beta spending function
- IA time point of 50% of total 266 completers, which yields 133 subjects who completed the Week 48 visit and have ALSFRS data.
- P-value for final analysis of 0.025

The above assumptions yielded a futility Stopping rule boundary of conditional power <42.5% assuming the effect for unobserved data will be the same as alternative hypothesis in the design stage (namely, 2.6).

The Statistical Simulation Result by EAST Software Version 6

Study Plan	True Delta (SD)	Power	Probability to Stop	Average Sample Size
Fixed ^a	2.6 (7.0)	85.5%	No applicable	No applicable
Simulation 1	2.6 (7.0)	84.5%	4.5%	260.1
Simulation 2	2 (7.0)	63.4%	11.3%	250.9
Simulation 3	1 (7.0)	21.1%	35.3%	219.1
Simulation 4	0 (7.0)	2.4%	67.1%	176.8

a. NOTE: SAS software 9.4

The simulation results shows that the probability of stopping the study for futility under the alternative hypothesis on delta of 2.6 and the null hypothesis on delta of 0 is 4.5% and 67.1% respectively.

Given the IA results for comparing oral edaravone 105mg daily versus oral edaravone 105 mg oral on/off (details will be specified in a separate SAP), the conditional power to reach statistical significance at the end of the study will be computed. This conditional power will assume that the delta for unobserved data will follow 2.6 units as assumed in the design stage. The computed conditional power will be compared to the above specified stopping rule.

Recommended Decision Making Process

- If the calculated conditional power will meet this futility rule (i.e. Conditional Power < 42.5%), then, Independent Data Monitoring Committee (IDMC) will recommend to “Halt the study due to futility on the primary endpoint”.
- The IDMC will also perform IA for secondary efficacy endpoint, other efficacy endpoints, and safety endpoints in an exploratory manner.
- The IDMC will also look at ALSFRS data for the ongoing patients
- The IDMC will review all endpoints result and recommend the following
 - Halt the study if futility is observed or
 - Continue the study until completion.

As the above IA does not allow the early stopping of the study for proven efficacy, there will be no impact on the type I error for the final analysis. That is, the Sponsor will maintain the type I error for final analysis on 1-sided 0.025.

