3.2. Study Estimands

3.2.1. Primary Estimand

As pre-defined in the protocol (V5.0), if more than a few death events ($\geq 5\%$ death percentage for all randomized subjects, e.g., ≥ 19 death events) are observed in this study, an alternative primary estimand as well as primary endpoint will be used to incorporate death cases as Intercurrent Events (ICE). It was confirmed that the threshold of 19 death cases was crossed in the blinded data review meeting and therefore, the following back-up estimand will be used with CAFS being the primary endpoint.

The primary estimand construction elements are:

- Treatment of interest: The initially randomized treatment – Group 1 edaravone daily to be compared with Group 2 edaravone on/off during 48-week period.
- Population: Subjects with ALS as defined in the analysis set.
- Variable: CAFS score at Week 48.
- ICEs handling strategy
 - ICE1 – Additional/new AMX0035 treatment during the 48-week double-blind treatment period will be handled using treatment policy strategy.
 - ICE2 – Early discontinuation during the 48-week double-blind treatment period will be handled using hypothetical strategy.
 - ICE3 – Death will be handled within CAFS score derivation using composite variable strategy.
- Population-level summary: Mean difference in the variable (as specified above) between the 2 randomized groups – Group 1 edaravone daily vs Group 2 edaravone on/off.

The treatment effect will be attributed regardless of the use of additional/new AMX0035 treatment (ICE1) and as if early discontinuation events did not occur (ICE2), accounting for Death event (ICE3).

Note: If death after early discontinuation (ICE2) was occurred, the death event will be included.

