3.3.3. Other Secondary Endpoints

The following efficacy endpoints are defined as 'other' secondary:

- Change from baseline in ALS Functional Rating Scale-Revised (ALSFRS-R) score at Weeks 4, 8, 12, 24, 36, and 48
- Change from screening and baseline in % forced vital capacity (FVC) at Weeks 24 and 48
- Change from baseline in %SVC at Weeks 4, 8, 12, 24, and 36
- Change from baseline in ALSAQ40 to Week 24
- Change from baseline in body weight score at Weeks 4, 8, 12, 24, 36, and 48
- CAFS score at Weeks 24
- King's ALS Clinical Stage derived from ALSFRS-R score and death

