4. STUDY DESIGN

4.1. Study Design

This is a Phase 3b, multicenter, double-blind, parallel group, randomized, study that will evaluate the efficacy and safety of 2 treatment regimens of edaravone for a period of 48 weeks in subjects with ALS as follows:

- Group 1: Edaravone 105 mg oral dose once daily for 48 weeks
- Group 2: Edaravone 105 mg oral dose in for 14 days, followed by a 14-day placebo. Subsequently, repeat edaravone 105 mg oral dose in for 10 days followed by 18-day placebo (regimen denoted as on/off).

Eligible subjects will be randomized at baseline in a 1:1 ratio to receive 1 of 2 treatment groups. Randomization will be stratified according to ALSFRS-R rate of decline score for 8 weeks screening period (2 levels strata of -1,-2 or -3,-4) and geographical region (3 levels strata of Europe, America or Asia Pacific).

Concomitant use of riluzole is permitted when the doses and regimens will remain unchanged from the day of evaluation of ALSFRS-R at the screening visit, through the end-of-treatment (EOT) or early termination (ET). Although dose reduction, dose interruption or discontinuation due to the onset of AEs, progression of dysphagia, or gastrostomy while on oral edaravone 105 mg are allowed, it is prohibited to initiate the use of riluzole. Subjects who initiate riluzole therapy de-novo during the treatment period will be discontinued from the study. The use of AMX0035 will be allowed for patients in the event that it becomes commercially available via prescription in their respective country. AMX0035 should be taken at least 1 hour after MT-1186.

This study consists of a screening period of 8 weeks, a double blind treatment period of 48 weeks, and a safety follow-up period of 2 weeks. A schedule of assessment of all study procedures is provided in Table 1.

- **Screening period:** Screening assessments will be performed up to 8 weeks (\pm 7 days) prior to Day 1. All screening evaluations must be completed and reviewed to confirm that potential subjects meet all eligibility criteria. If a subject has not met all eligibility criteria at the end of the screening period, the subject will be registered as a screen fail. Screen fail subjects may be eligible for re-screening 1 time.
- **Double-blind Treatment Period:** Subjects who successfully complete the screening period will return to the study clinic on Day 1 in a fasting state (eg, without breakfast) and inclusion

Statistical Analysis Plan
Protocol No. MT-1186-A02

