4.2. Sample Size and Power Considerations

Assuming the use of a t-test, a 2-sided alpha level of 5% and a 30% dropout rate up to Week 48, a sample size of 190 subjects per groups (380 subjects in total) will provide 85.5% power to detect an effect size of 0.37 (ie, an absolute treatment difference of 2.6 with an associated standard deviation [SD] of 7) in the change from baseline in ALSFRS-R score to Week 48 between edaravone 105 mg oral dose once daily versus edaravone 105 mg oral dose on/off regimen; see details in Appendix 1.

A sample size of 190 subjects per groups will have 78% power to detect statistically significant result for the time to death, tracheostomy, or permanent assisted mechanical ventilation. This calculation assumed a true hazard ratio between edaravone 105 mg daily (test) to edaravone 105 mg on/off regimen (control) of $HR=0.3$. Namely, 70% reduction in the hazard assuming 90% survival rate at Week 48 for the control group. This calculation assumes 2-sided alpha of 5% using the log-rank test and follow-up time of 48 weeks.

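### SAP Appendix 1 describes the futility rule as one on the primary endpoint, but its boundary and operating characteristics belong to ALSFRS-R change, which the same SAP has replaced with CAFS

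*SAP*

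**What the plan says.** SAP 3.2.1 reports that the blinded data review found the death threshold crossed and that "the following back-up estimand will be used with CAFS being the primary endpoint". SAP 3.3.1, 7.3 (H01) and 9.2.1.1 follow: the final test is an ANCOVA on CAFS ranks at Week 48 after multiple imputation. SAP 3.3.3 lists "Change from baseline in ALS Functional Rating Scale-Revised (ALSFRS-R) score at Weeks 4, 8, 12, 24, 36, and 48" among the other secondary endpoints.

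SAP 5.1 announces one futility interim, in the future tense, and refers to Appendix 1 for the boundary. Appendix 1 gives the design inputs as "One sided type I error of 0.025" and "Delta of 2.6 units in ALSFRS between Test group to control group with SD of 7.0", with 266 completers in total and an interim at 133 who have Week 48 ALSFRS data. The resulting boundary is conditional power below 42.5%. On the drift it says "This conditional power will assume that the delta for unobserved data will follow 2.6 units as assumed in the design stage". If the boundary is met, the IDMC is to recommend "Halt the study due to futility on the primary endpoint".

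SAP section 11, which lists changes from the protocol, does not mention the interim.

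**The concern.** Conditional power should be the probability, given the interim data, that the final primary test succeeds. Appendix 1 describes its quantity in those terms, but calculates it for a different test. The ALSFRS-R statistic at Week 48 uses survivors with a score. CAFS ranks every death below every survivor, so a survival difference moves CAFS without moving the ALSFRS-R statistic.

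Two things are at stake. First, anyone reading the 4.5% false-stop risk and 84.5% power as properties of this trial's primary analysis would be misled. Second, if the interim is still to come and the text is followed literally, a halt labelled as primary-endpoint futility would rest on an endpoint ranked other secondary.

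**Working it through.** **Inputs from the documents.** SAP 4.2: t-test with "a 2-sided alpha level of 5% and a 30% dropout rate up to Week 48", 190 per group. SAP 4.1: "Eligible subjects will be randomized at baseline in a 1:1 ratio to receive 1 of 2 treatment groups". SAP Appendix 1: difference 2.6, SD 7.0, 266 completers (2 × 190 × 0.7), interim at 133 (t = 0.5), boundary 42.5%.

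**Step 1: reproduce the plan's figures as an ALSFRS-R mean-difference test.**
- Drift at full information: θ = 2.6 / (7 × √(2/133)) = 3.029.
- Fixed-design power with 133 per arm: 85.5% (noncentral t, 264 df). Stated: 85.5%.
- Conditional power: CP = Φ[(Z₁√t + θ(1−t) − 1.96) / √(1−t)]. At t = 0.5 this is Φ(Z₁ − 0.630).
- CP = 0.425 gives Z₁ = 0.630 − 0.189 = 0.441, an observed difference of 0.441 × 7 × √(2/66.5) = 0.54 points.
- Stop probability: Φ(0.441 − θ_δ√0.5), where θ_δ is the drift at true difference δ. Power is from the bivariate normal of the interim and final Z.

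| True difference | Stop, computed | Stop, stated | Power, computed | Power, stated |
|---|---|---|---|---|
| 2.6 | 4.4% | 4.5% | 84.5% | 84.5% |
| 2 | 11.4% | 11.3% | 62.9% | 63.4% |
| 1 | 35.1% | 35.3% | 20.5% | 21.1% |
| 0 | 67.0% | 67.1% | 2.4% | 2.4% |

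The table and the 42.5% boundary are therefore those of an ALSFRS-R mean-difference test with no death component.

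**Step 2: can the same be done for CAFS?** No. The documents give no CAFS effect, variance, drift or boundary. Nor is 133 of 266 completers necessarily half the CAFS information, because SAP 8.4.2.1 also brings in deaths and subjects with imputed Week 48 scores. The blinded review shows only that pooled deaths reached about 5% (0.05 × 380 = 19). It says nothing about the split between arms.

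**Step 3: illustration under assumed inputs.** 95 randomised per arm (half of the 190 in SAP 6.1.7), 25% dropout other than death, normal ALSFRS-R change with SD 7, and the boundary Z = 0.441 applied to both statistics. CAFS is approximated by ranks of deaths plus completers, without imputation or covariates. Simulations used about 4,000 runs. The strong-benefit case takes 90% control survival and HR 0.3, so deaths are 10% against 1 − 0.9^0.3 = 3.1%. SAP 4.2 attaches those values to the composite of death, tracheostomy or permanent ventilation, so using them for death alone is an assumption. Each cell is stop probability, ALSFRS-R vs CAFS.

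| Deaths, on/off vs daily | Death-function correlation | 2.0 points | 1.5 points |
|---|---|---|---|
| 10% vs 3.1% | 0 | 11.6% vs 3.4% | 21% vs 6% |
| 10% vs 3.1% | 0.5 | 18% vs 5% | 31% vs 10% |
| 10% vs 3.1% | 0.8 | 22% vs 6% | 39% vs 13% |
| 10% vs 8.1% (HR 0.8) | – | about 12% vs 13% | about 23% vs 21% |

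With equal 5% deaths the order reverses: about 10-11% vs 14% at 2.0 points, and about 4% vs 6% at 2.6 points. With no effect on either outcome, both rules stop in about 66-68% of trials.

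**Step 4: a stricter measure of harm.** A separate simulation (133 per arm, 3,000 runs per scenario, deaths independent of function, control survival 95% or 90%, HR 1 to 0.3, differences 0 to 2.6) estimated how often the ALSFRS-R rule stops a trial whose CAFS test would have been significant. The range was 0.2% to 8%. The maximum, 7.8%, came at 1 point, HR 0.3 and 90% control survival.

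**The case against.** The strongest reply is about timing. The switch depended on deaths among all randomised subjects. The only blinded review meeting that the SAP places in time (8.4.1.1) comes before database lock, and 5.2 puts lock after SAP sign-off. The interim needs only the first 133 Week 48 completers and uses the first 190 randomised (6.1.7). It may well have come first. ALSFRS-R change was then the protocol's default primary endpoint (Protocol 17.1.1), the rule matched it, and Appendix 1, which largely repeats Protocol Appendix 6, is design text carried forward. This stands: neither event is dated.

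There are also safeguards. The rule is non-binding. The IDMC is to look at secondary, other and safety endpoints, and time to death is a key secondary, so survival would be seen. A separate futility SAP and an IDMC charter, neither supplied, may name the endpoint. These reduce the practical risk. They do not correct this SAP, whose Appendix 1 does not list Week 48 CAFS among the results for the IDMC.

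A reader might infer that the IDMC was, or will be, told to halt on the wrong endpoint. The documents do not support that, because the order of events and the governing futility SAP are unknown. A reader might also infer that the ALSFRS-R rule generally stops too readily. That is not supported either: the direction depends on the survival effect.

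**Conclusion.** The mismatch is on the page and does not depend on timing. SAP Appendix 1 attributes to the primary endpoint a boundary and a set of operating characteristics that belong to ALSFRS-R change. Followed literally, the rule does not give the conditional power of the final CAFS test.

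Its consequence is uncertain. With a strong survival benefit (10% vs 3.1% deaths) and a 2.0-point difference, the ALSFRS-R rule stops in about 12-18% of trials and a CAFS rule in about 3-5%, for death-function correlations from 0 to 0.5. With similar deaths in the two arms, the ALSFRS-R rule stops about equally or somewhat less often. These figures rest on assumed death rates, dropout and correlation, and on borrowing the ALSFRS-R boundary for CAFS. If the interim preceded the switch, what remains is a labelling fault with no bearing on the halt decision.

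**What to change.** State in SAP 5.1 and Appendix 1 whether the interim came before the switch to CAFS.

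- **If it did:** put Appendix 1 in the past tense, name ALSFRS-R change as the endpoint tested, confine the tabulated stop probabilities and power to it, and delete the reference to the primary endpoint in the halt recommendation.
- **If it is still to come:** either (a) define a CAFS drift, information fraction and boundary and retabulate the operating characteristics, or (b) relabel the rule as futility on ALSFRS-R change and require the interim CAFS result to be shown to the IDMC beside it before any halt recommendation. Option (a) should not simply reuse 42.5%, which was derived from 2.6 points, SD 7 and 266 completers. Option (b) needs no new assumption.

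Record the choice in SAP section 11 and align the separate futility SAP.

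The cost is minor rewording and, if the interim is pending, one additional statistic; option (a) also needs a stated CAFS effect and new design calculations. Type I error is unaffected because the rule is non-binding and allows no early efficacy claim.

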APPENDIX 2: SMQ LIST

Peripheral Neuropathy

PT Name	PT Number
Acute painful neuropathy of rapid glycaemic control	10072909
Acute polyneuropathy	10066699
Amyotrophy	10002027
Angiopathic neuropathy	10079036
Anti-myelin-associated glycoprotein associated polyneuropathy	10078324
Autoimmune neuropathy	10070439
Axonal neuropathy	10003882
Biopsy peripheral nerve abnormal	10004846
Decreased vibratory sense	10067502
Demyelinating polyneuropathy	10061811
Guillain-Barre syndrome	10018767
Immune-mediated neuropathy	10078963
Ischaemic neuropathy	10051307
Joint position sense decreased	10081223
Loss of proprioception	10057332
Miller Fisher syndrome	10049567
Multifocal motor neuropathy	10065579
Myelopathy	10028570
Nerve conduction studies abnormal	10029175
Neuralgia	10029223
Neuritis	10029240
Neuronal neuropathy	10071579
Neuropathic muscular atrophy	10075469
Neuropathy peripheral	10029331
Notalgia paraesthesia	10072643
Paroxysmal extreme pain disorder	10081856
Peripheral motor neuropathy	10034580
Peripheral nervous system function test abnormal	10034591
Peripheral sensorimotor neuropathy	10056673
Peripheral sensory neuropathy	10034620
Polyneuropathy	10036105
Polyneuropathy chronic	10064135

Statistical Analysis Plan
Protocol No. MT-1186-A02

Mitsubishi Tanabe Pharma America, Inc.

Polyneuropathy idiopathic progressive	10036111
Radiation neuropathy	10068886
Sensorimotor disorder	10062162
Sensory disturbance	10040026
Sensory loss	10040030
Small fibre neuropathy	10073928
Tick paralysis	10077336
Toxic neuropathy	10067722
Anti-ganglioside antibody positive	10072516
Anti-myelin-associated glycoprotein antibodies positive	10078318
Areflexia	10003084
Autonomic failure syndrome	10056339
Autonomic neuropathy	10061666
Burning feet syndrome	10070237
Burning sensation	10006784
Decreased nasolabial fold	10076861
Dysaesthesia	10013886
Electromyogram abnormal	10014431
Formication	10017062
Gait disturbance	10017577
Genital hypoesthesia	10068912
Hereditary motor and sensory neuropathy	10077306
Hypoesthesia	10020937
Hyporeflexia	10021089
Hypotonia	10021118
Mononeuritis	10027910
Mononeuropathy	10062203
Mononeuropathy multiplex	10027918
Motor dysfunction	10061296
Muscle atrophy	10028289
Muscular weakness	10028372
Nerve degeneration	10056677
Neuromuscular pain	10074313
Neuromuscular toxicity	10062284
Neuromyopathy	10029323

Statistical Analysis Plan
Protocol No. MT-1186-A02

Mitsubishi Tanabe Pharma America, Inc.

Neuropathy vitamin B12 deficiency	10079953
Neuropathy vitamin B6 deficiency	10029332
Neurotoxicity	10029350
Paraesthesia	10033775
Paraesthesia ear	10052433
Peripheral nerve lesion	10067633
Peripheral nerve palsy	10058530
Peripheral nerve paresis	10071663
Peroneal nerve palsy	10034701
Phrenic nerve paralysis	10064964
Skin burning sensation	10054786
Synkinesis	10078747
Temperature perception test decreased	10068015
Tinel's sign	10052492
Ulnar neuritis	10045380

COVID-19

PT Name	PT Number
Asymptomatic COVID-19	10084459
Coronavirus infection	10051905
Coronavirus test positive	10070255
COVID-19	10084268
COVID-19 immunisation	10084457
COVID-19 pneumonia	10084380
COVID-19 prophylaxis	10084458
COVID-19 treatment	10084460
Exposure to SARS-CoV-2	10084456
Multisystem inflammatory syndrome in children	10084767
Occupational exposure to SARS-CoV-2	10084394
SARS-CoV-2 antibody test positive	10084491
SARS-CoV-2 carrier	10084461
SARS-CoV-2 sepsis	10084639
SARS-CoV-2 test false negative	10084480
SARS-CoV-2 test positive	10084271
SARS-CoV-2 viraemia	10084640

Statistical Analysis Plan
Protocol No. MT-1186-A02

Mitsubishi Tanabe Pharma America, Inc.

Suspected COVID-19	10084451
Antiviral prophylaxis	10049087
Antiviral treatment	10068724
Coronavirus test	10084353
Coronavirus test negative	10084269
Exposure to communicable disease	10049711
Pneumonia viral	10035737
SARS-CoV-2 antibody test	10084501
SARS-CoV-2 antibody test negative	10084509
SARS-CoV-2 test	10084354
SARS-CoV-2 test false positive	10084602
SARS-CoV-2 test negative	10084273
